#### 1. **OVERVIEW**

The purpose of the statistical analysis plan (SAP) is to ensure the credibility of the study results by pre-specifying the statistical approaches for the analysis of study data prior to database lock. The SAP is intended to be a comprehensive and detailed description of the strategy and statistical methods to be used in the analysis of data collected in R4461-PLD-20100 study.

This plan may be revised during the study to accommodate protocol amendments and adapt to unexpected issues in study execution that may affect planned analyses. These revisions will be based on data review, and a final plan will be issued prior to the final database lock.

# 1.1. Background/Rationale

This Phase 2, randomized, double-blind, placebo-controlled study is designed to evaluate the efficacy and safety of mibavademab (or REGN4461) in patients with familial partial lipodystrophy and metabolic abnormalities (elevated fasting TG with or without elevated HbA1c) who are not receiving rhLeptin (metreleptin) therapy. This study will compare the efficacy and safety of mibavademab to placebo.

Lipodystrophy is a rare condition in which the body is unable to produce or maintain adipose tissue. Partial lipodystrophy (PLD) is characterized by the selective loss of adipose tissue from various areas of the body. Partial lipodystrophy is a heterogeneous disease, and the extent of lipoatrophy varies significantly among patients. The reduced number of functional adipocytes can lead to relative leptin deficiency and associated metabolic abnormalities due to lipids being stored in other tissues, including muscle and liver. These metabolic abnormalities include hypertriglyceridemia, insulin resistance/diabetes, and nonalcoholic fatty liver disease. Partial lipodystrophy patients with diabetes are at increased risk for complications of diabetes, including nephropathy. In a large fraction of familial partial lipodystrophy (FPLD) patients (one-third to one-half, based on available data), lipoatrophy is extensive enough to result in reduced leptin levels (<8.0 ng/mL), which could drive severe hunger and insulin resistance.

The true incidence of PLD is unknown, with estimates of 2 to 3 clinical cases per million (Chiquette, 2017). Most cases of PLD are familial (FPLD), and often are associated with pathogenic mutations in genes important for adipocyte biology. However, due to a presentation that overlaps with the much more common metabolic syndrome, FPLD is clinically underdiagnosed. Recent data point to a higher prevalence of individuals with FPLD gene variants, as high as 160 per million (Gonzaga-Jauregui, 2020).

Mibavademab is a human antibody that binds and activates the leptin receptor (LEPR) independent of leptin binding. Mibavademab is not related to endogenous leptin, and therefore should not have the risk of anti-drug antibodies (ADAs) cross-reacting with and neutralizing endogenous leptin.

Based on preclinical and clinical studies performed to-date, it is hypothesized that low-leptin familial PLD (FPLD) patients will benefit from treatment with mibavademab, and therefore FPLD patients with a range of lower leptin levels will be enrolled to explore the relationship between leptin levels and response to mibavademab in this study. The primary analysis of this study includes FPLD patients with leptin levels <8.0 ng/mL (Cohort A). A second cohort of FPLD patients with leptin levels of 8.0 ng/mL to ≤20.0 ng/mL (Cohort B) will also be assessed (separately) given analyses of individualized patient data from the National Institutes of Health (NIH), which indicated that patients with leptin ≤20.0 ng/mL had a better response to metreleptin

Regeneron Pharmaceuticals, Inc.

Page 12 of 88

Protocol: R4461-PLD-20100

than did those with leptin >20.0 ng/mL. An analysis of the combined set of cohorts A plus B (also named as combined Cohort A+B that includes all patients in Cohort A and Cohort B) will also be performed to determine the effect of mibavademab on endpoints in patients with leptin levels within the broader range ( $\leq$ 20.0 ng/ml). An Investigational Use Only (IUO) leptin assay (ie, investigational human leptin assay) is being developed for stratification and patient selection purposes; study eligibility and cohort allocation will be determined using this leptin Enzyme Linked Immunosorbent Assay (ELISA) developed and validated under Clinical Laboratory Improvement Amendments (CLIA) guidelines.

Additional background information on the study drug and development program can be found in the Investigator's Brochure.

# 1.2. Study Objectives

# 1.2.1. Primary Objectives

The primary objectives will be evaluated for patients in cohort A (leptin  $\leq 8.0 \text{ ng/ml}$ ) only:

- To evaluate the effect of mibavademab on fasting TG in patients with baseline leptin <8.0 ng/mL and with elevated baseline fasting TG (>200 mg/dL)
- To evaluate the effect of mibavademab on hyperglycemia in patients with baseline leptin <8.0 ng/mL and with elevated baseline HbA1c (>7.0%)

# 1.2.2. Secondary Objectives

The following secondary objectives of the study will be evaluated for cohort B and for the combined set of cohorts A plus B:

- To evaluate the effect of mibavademab on fasting TG levels in patients with hypertriglyceridemia (screening fasting TG >200 mg/dL)
- To evaluate the effect of mibavademab on glycemic control in patients with hyperglycemia (screening HbA1c >7.0%)

The following secondary objectives of the study will be evaluated for cohorts A and B separately, and for the combined set of cohorts A plus B:

- To evaluate the effect of mibavademab on liver fat in patients with hepatic steatosis (baseline Hepatic Fat Fraction [Magnetic resonance imaging-derived proton density fat fraction, MRI-PDFF]  $\geq 8.5\%$ )
- To evaluate the effect of mibavademab on hunger
- To evaluate safety and tolerability of mibavademab
- To characterize the concentration profile of mibavademab over time
- To assess immunogenicity to mibavademab

## 1.2.3. Exploratory Objectives

The exploratory objectives of the study, will be evaluated for cohorts A and B separately, and for the combined set of cohorts A plus B:

Regeneron Pharmaceuticals, Inc.

Page 13 of 88

Protocol: R4461-PLD-20100

- To evaluate the effect of mibavademab on insulin sensitivity
- To evaluate the effect of mibavademab on pain
- To evaluate the effect of mibavademab on depression
- To evaluate the effect of mibavademab on anxiety
- To evaluate the effect of mibavademab on body weight
- To evaluate the effect of mibavademab on regional body composition
- To evaluate the effect of mibavademab on Quality of Life (QoL)
- To study the activity of mibavademab (including biomarker discovery related to safety and efficacy of mibavademab), the leptin pathway and FPLD (including insulin resistance, hepatic steatosis, and hypertriglyceridemia)
- To determine if bioimpedance measurements can be used as adequate surrogates for dual-energy X-ray absorptiometry (DXA) to measure regional body composition in patients with FPLD

#### 1.2.4. Modifications from the Statistical Section in the Final Protocol

The content of this SAP reflects the content of the statistical section of Protocol R4461-PLD-20100 Amendment 1 with the following exceptions:

- Protocol Section 4. Endpoints: The definitions of endpoints are clarified in SAP Section 5.7 by replacing:
  - "elevated baseline fasting TG" into "screening TG"
  - "elevated baseline HbA1c" for defining subgroup into "screening HbA1c" to match HbA1c strata (screening HbA1c ≤7.0%, >7.0%)
  - "baseline leptin" for defining Cohort into "screening leptin"
- Protocol Section 11.3.2. Safety Analysis Set: Safety analysis set (SAF) is replaced with DB SAF and SB SAF as follows in SAP Section 3.2:
  - DB SAF includes all randomized patients who received any double-blind study drug.
  - SB SAF includes all the patients in the double-blind SAF who also received at least 1 study drug in the single-blind treatment period.
- Protocol Section 11.4.5.4. Treatment Compliance: Compliance % calculation is replaced with study treatment administration interval compliance in SAP Section 5.8.8.
- Protocol Section 11.4.3. Efficacy Analyses: The randomization strata per IVRS in the analysis models (eg, MMRM) are replaced with actual strata in SAP Section 5.7 to reflect the actual disease characteristic for statistical modeling.
- Protocol Section 11.4.3. Efficacy Analyses: Due to the early termination of the study and subsequent limited number of participants enrolled, only descriptive summaries

Protocol: R4461-PLD-20100

and line plots for fasting TG, HbA1c, fasting glucose, liver fat (MRI-PDFF), and Daily Lipodystrophy Hunger Questionnaire (DLHQ) over time will be provided by treatment group. Spaghetti plots for fasting TG, HbA1c, fasting glucose, liver fat (MRI-PDFF), and DLHQ will be provided for individual patient data across visits for the endpoints by treatment group if applicable.

Protocol: R4461-PLD-20100

Date: May 16, 2024

• SAP Section 7 Timing of Statistical Analyses: First Step Analysis and Second Step Analysis will not be performed.

# 1.2.5. Revision History for Statistical Analysis Plan Version 1

This is the original version of the SAP.

## 2. INVESTIGATION PLAN

# 2.1. Study Design and Randomization

The study consists of the following 5 periods (Figure 1):

- A screening period up to 10-weeks
- A placebo run-in period (PBO) for 4 weeks
- A randomized double-blind placebo-controlled treatment period (TP1 or DBTP) for 12 weeks
- A single-blind treatment period (TP2 or SBTP) during which all patients receive mibavademab for 12 weeks
- An off-drug safety follow-up period for 16 weeks

Figure 1: Study Flow Diagram

Patients 18 years of age or older with a clinical diagnosis of FPLD will undergo screening, including measurement of HbA1c, fasting TG, and leptin levels. A diagnosis of FPLD requires either a documented ClinVar pathogenic or likely pathogenic variant in a known FPLD gene or pathognomonic regional lipoatrophy by DXA. In addition, patients must have metabolic abnormalities (elevated fasting TG with or without elevated HbA1c) and leptin level ≤20.0 ng/mL to be included.

After the screening period of up to 10 weeks, eligible patients will be assigned to one of the following two leptin cohorts based on the mean screening leptin levels:

Regeneron Pharmaceuticals, Inc.

Page 15 of 88

- Cohort A: FPLD patients with serum leptin <8.0 ng/mL
- Cohort B: FPLD patients with serum leptin 8.0 to ≤20.0 ng/mL

Then, these patients will begin the single-blind 4-week placebo run-in period.

On Day 1 after the placebo run-in period, each cohort of patients will be centrally randomized via interactive voice response system (IVRS) in a 1:1 ratio to Arm 1 or Arm 2:

- Arm 1: placebo
- Arm 2: mibayademab

Subjects will be stratified based on screening HbA1c (HbA1c  $\leq$ 7% or HbA1c  $\geq$ 7%) to ensure equal representation of patients with elevated HbA1c in each study arm. Schedules of study treatments and follow-up periods are summarized in Table 1.

**Table 1: Summary of Study Arms** 

		Arm 1	Arm 2	
Double- blind	Day 1 (IV loading dose based on weight)	Placebo IV	mg/kg mibavademab IV	
Treatment Period (DBTP)	Day 8 onwards (for 11 weekly maintenance doses)	Placebo SC QW	mg mibavademab SC QW	
Single- blind Treatment Period (SBTP)	Day 85 (IV loading dose based on weight)	■ mg/kg mibavademab IV followed by Placebo SC	Placebo IV followed by mg mibavademab SC	
	Day 92 (for 11 weekly doses)	mg mibavademab SC QW		
	Day 169 until week 40	Off-Drug Safety Follow-up		

The study event table is presented in Appendix 10.7.

# 2.2. Justification of Sample Size

The size of the study is determined by feasibility assessments. Due to the limited number of identified FPLD patients with low leptin and moderate metabolic abnormalities, up to 40 patients will be enrolled.

With a total of 40 patients (20 per cohort, randomized in the ratio of 1:1 into Arm 1 and Arm 2), the primary analysis will be carried out on the 20 patients in the lower leptin Cohort A in DBTP. The fact that it is unlikely that all of the patients will have HbA1c >7.0%, ie, not all of the patients will be assessed for the HbA1c endpoint, has also been accounted for. From the feasibility work, it is estimated that 78% of the patients will have elevated screening HbA1c. With 20 patients in Cohort A (10 patients per study arm; Table 2), the half-width of the 90% confidence interval of the difference in change from baseline to week 12 between Arm 1 and Arm 2 for HbA1c is 1.4 percentage points, assuming a SD of 1.81%. For TG, the half-width of the 90% confidence interval

Regeneron Pharmaceuticals, Inc.

Page 16 of 88

Protocol: R4461-PLD-20100

in logarithm-transformed geometric mean ratio (GMR) (mibavademab week12/baseline divided by placebo week12/baseline) is 0.67, assuming the SD for logarithm-transformed fasting TG is 0.87. The SD estimates are from the FPLD subset samples of the extracted NIH study data (Diker-Cohen. 2015).

Table 2: Half-Width of the 90% Confidence Interval for Primary Endpoints

Endpoint	Number of Patients per Group in the Subset	Half of the 90% confidence interval**	
HbA1c*	7	1.72%	
	8	1.59%	
HbA1c †	10	1.4%	
Fasting TG †	10	0.67	

\*Assuming 78% of the patients have elevated screening HbA1c.

# 3. ANALYSIS POPULATIONS

In accordance with guidance from the International Conference of Harmonization of Technical Requirements for Registration of Pharmaceuticals for Human Use (ICH) guideline ICH E9 Statistical Principles for Clinical Trials (ICH, 1998), below are the patient populations defined for statistical analysis. The efficacy analysis population is the full analysis set. Additional patient populations include safety analysis sets, pharmacokinetic analysis set, immunogenicity analysis set, and clinical outcome assessment set. For the purposes of the definitions below, a patient is considered randomized to study treatment when they have been screened and received a randomization number and are recorded in the IVRS/IWRS database.

# 3.1. Efficacy Analysis Sets

# 3.1.1. Full Analysis Set (FAS)

The full analysis set (FAS) includes all randomized patients who received any study drug in DBTP and have at least 1 post-baseline assessment. Patients in the FAS population will be analyzed according to the treatment group allocated by randomization (as-randomized). Efficacy endpoints will be analyzed using the FAS.

# 3.2. Safety Analysis Sets (SAF)

## 3.2.1. Double-Blind Safety Analysis Set

The double-blind safety analysis set (DB SAF) includes all randomized patients who received any double-blind study drug. Patients will be analyzed according to the treatment received (as treated). Treatment compliance/administration and all clinical safety variables will be analyzed using the double-blind SAF.

Regeneron Pharmaceuticals, Inc.

Page 17 of 88

Protocol: R4461-PLD-20100

\*\*The estimates of treatment effects of drug at the end of the DBTP (week 12) are -1.18% for HbA1c, and -52% for fasting TG. After adjusting for placebo effect, the between-group treatment effect estimates are -0.98% for HbA1c, and -47% for fasting TG. SD for HbA1c is assumed to be 1.81%, and for logarithm-transformed fasting TG is assumed to be 0.87 (SD estimates extracted from NIH study data).

<sup>†Assuming all patients have baseline HbA1c >7.0% and TG >200 mg/dL.

In addition:

• Randomized patients for whom it is unclear whether they took the study drug will be included in the DB SAF as randomized.

Protocol: R4461-PLD-20100

Date: May 16, 2024

• For randomized patients receiving both mibavademab and placebo study treatment in the DBTP, the treatment group allocation for as-treated analysis will be mibavademab.

# 3.2.2. Single-Blind Safety Analysis Set

The single-blind safety analysis set (SB SAF) includes all randomized patients who received any single-blind study drug.

# 3.3. Pharmacokinetic (PK) Analysis Set

The PK analysis set is defined as all randomized patients who received any study drug and have at least 1 non-missing measurement of mibavademab concentration following the first dose of study drug. Treatment assignments for DBTP are based on the actual treatment received (as treated).

# 3.4. Immunogenicity Analysis Set

The ADA analysis set includes all treated patients who received any amount of study drug (active or placebo) and had at least one non-missing anti-drug antibody result following the first dose of study drug. The ADA analysis set is based on the actual treatment received (as treated).

#### 3.5. Clinical Outcome Assessment

The analyses for Clinical Outcome Assessments (COA) will be performed on all randomized patients who received any study treatment. Patients will be analyzed according to the treatment received (as treated). Further for each scale:

- For the daily lipodystrophy hunger questionnaire, patients will be included when a baseline and at least one-week post-baseline scores are available.
- For the remaining COA item (eg, quality-of-life questionnaire, etc.), patients will be included when a baseline and at least one post-baseline score is available.

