# 4.7. Efficacy Variables

Efficacy will be assessed through the following parameters: fasting TG, HbA1c, fasting glucose, liver fat content as measured by MRI-PDFF, and lipodystrophy hunger questionnaire outcomes.

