### 5.12. Analysis of Clinical Outcome Assessment

The summary of results for clinical outcomes assessments will be presented by treatment groups (Arm 1, Arm 2) and by cohorts (Cohort A, Cohort B) containing patients from the full analysis set, unless otherwise specified.

The baseline value is defined as the last available measurement prior to the time of the first double-blind study treatment administration. All measurements, scheduled or unscheduled, will be assigned to the Global Analysis Windows (Appendix 10.2) to provide an assessment for all post-baseline visit.

For the SF-36, raw value and change from baseline will be summarized using mean, median, SD, min, max, Q1, Q3 for each post baseline visit among the SF-36 analysis set.

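### SAP 3.5 groups the hunger questionnaire, a secondary efficacy endpoint, as treated, while SAP 3.1.1, SAP 5.7.2 and Protocol 11.3.1 require the as-randomised FAS

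*SAP*

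**What the plan says.** **The as-treated rule.** SAP 3.5 sets the population: "The analyses for Clinical Outcome Assessments (COA) will be performed on all randomized patients who received any study treatment". It then sets the grouping: "Patients will be analyzed according to the treatment received (as treated". Its first sub-rule concerns hunger: "For the daily lipodystrophy hunger questionnaire, patients will be included when a baseline and at least one-week post-baseline scores are available".

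**The as-randomised rule.** SAP 3.1.1 says of the FAS: "Patients in the FAS population will be analyzed according to the treatment group allocated by randomization (as-randomized". It adds: "Efficacy endpoints will be analyzed using the FAS". SAP 5.7.2 repeats the FAS for the secondary efficacy endpoints. Protocol 11.3.1 defines one efficacy set, the FAS, based on allocated treatment.

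**Where hunger belongs.** The efficacy parameters in SAP 4.7 end with "liver fat content as measured by MRI-PDFF, and lipodystrophy hunger questionnaire outcomes". SAP 4.7.2 lists change in the hunger questionnaire to week 12 and to week 24 as secondary endpoints.

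**The clinical outcome section.** SAP 5.12 presents these assessments by Arm 1 and Arm 2 and by cohort, "containing patients from the full analysis set, unless otherwise specified".

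**Declared departures.** SAP 1.2.4 lists changes from the protocol's statistical section, including the split safety sets and the use of actual strata. It lists no as-treated set for clinical outcome assessments. It also cuts efficacy output, hunger included, to descriptive summaries and plots by treatment group because the study was terminated early.

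**The concern.** A programmer cannot follow both SAP 3.5 and SAP 3.1.1 with 5.7.2 for the hunger questionnaire. If anyone was treated other than as randomised, the hunger summaries and plots could place that patient in one group while TG, HbA1c, glucose and liver fat place the same patient in the other. The as-treated version would also give up the comparability that randomisation provides, for a patient-reported efficacy endpoint. Because the choice is left open, it could be settled after the data have been seen.

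**Working it through.** No figure in the plan bears on this point, so the check is mainly a comparison of text, followed by one illustration of size.

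**1. Is hunger bound by both rules?** SAP 3.5 names it. SAP 4.7 and 4.7.2 make it an efficacy endpoint, so SAP 3.1.1 and 5.7.2 also bind it. Neither 3.1.1 nor 5.7.2 carries an exception.

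| | SAP 3.5 | SAP 3.1.1, applied by 5.7.2 |
|---|---|---|
| Treatment required | Any study treatment | Any study drug in the double-blind period |
| Data required | Hunger: baseline and at least one week of later scores | At least one post-baseline assessment |
| Grouping | As treated | As randomised |

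**2. Which difference can change a result?** The inclusion rules differ on paper but should select nearly the same patients for hunger. A patient without hunger scores adds nothing under either rule, and SAP 5.7.2.1 already sets a monthly average to missing when fewer than 10 scores are reported. The grouping row is the one that can matter.

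**3. When do the groupings differ?** Only when a patient received treatment other than that randomised. SAP 4.5 and 5.5 plan a listing of such patients. Neither document reports one.

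**4. What output is affected?** SAP 5.7.2.1 summarises hunger descriptively to week 12 and to week 24, with plots by treatment group. Hunger does not appear in SAP Tables 3 to 7, where the secondary models, estimates, differences and nominal p-values are set out.

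**5. Are the other assessments in the same position?** No. Pain, depression, anxiety and quality of life serve exploratory objectives (SAP 1.2.3) and are not listed in SAP 4.7, so 3.1.1 does not reach them. Their only conflict is with SAP 5.12.

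**6. Illustration of size.** Inputs: 10 patients per arm within a cohort (Protocol 6.1.1, planned). Let D be the true difference, drug minus placebo. Let d be the deviation of one placebo patient from the mean of the ten placebo patients. That patient is counted as drug, and the stray dose is assumed to have no effect. Take the mean of the ten placebo patients as zero.

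- As-treated drug mean: (10D + d)/11
- As-treated placebo mean: -d/9
- Difference: 10D/11 + d(1/11 + 1/9)
- Shift from D: -D/11 + d(1/11 + 1/9) = -0.09D + 0.20d

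The direction depends on that assumption. If the patient instead responds fully to drug and is otherwise average, the as-randomised difference is D - D/10 = 0.9D and the as-treated difference is (10D + D)/11 = D.

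**The case against.** The strongest defence is that this is a drafting slip with no demonstrated effect. No hunger test is planned, the output is descriptive, the two rules coincide unless someone was treated off allocation, and any such patient would appear in a listing. All of that stands, and it sets the rating. It does not tell the programmer which rule to apply.

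A second defence is that the exception clause in SAP 5.12 defers to 3.5. That may settle 5.12, and with it the assessments other than hunger. It cannot settle hunger, because 3.1.1 and 5.7.2 have no such clause.

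A reader might also draw three stronger conclusions that the documents do not support:

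- **That a dosing problem makes cross-arm treatment likely.** The sensitivity analysis in SAP 5.7.1.1 for a systemic dosing error concerns under-dosed patients. An under-dosed mibavademab patient is in the mibavademab group under both rules.
- **That one dose of drug moves a placebo patient in the hunger analysis.** The rule that "the treatment group allocation for as-treated analysis will be mibavademab" stands under the double-blind safety set in SAP 3.2.1. It covers patients given both treatments in the double-blind period, and SAP 3.5 does not cite it. Extending it to hunger is an inference.
- **That as-treated grouping always dilutes the effect.** The 1/11 loss is one term of the shift and holds only if the stray dose did nothing.

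**Conclusion.** Wrong as written: an internal contradiction, with low impact. For the hunger questionnaire, SAP 3.5 conflicts with SAP 3.1.1, SAP 5.7.2 and Protocol 11.3.1, and SAP 1.2.4 does not declare the departure. The consequence is limited to by-group descriptive summaries and plots, and arises only if a patient received treatment other than that randomised. A reader might infer that a formal randomised comparison is compromised; the SAP plans none for hunger.

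The 9-versus-11 arithmetic is an illustration at planned numbers, not an estimate of an error that occurred. SAP 1.2.4 says enrolment was limited, so the actual arms may be smaller and one patient may weigh more. For the other clinical outcome assessments the point is only that 5.12 and 3.5 should be made to agree.

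**What to change.** Reword SAP 3.5 so that clinical outcome assessments, at least the hunger questionnaire, are analysed in FAS patients who have a baseline score and the required post-baseline score on that scale, grouped by randomised arm (Arm 1 or Arm 2). Make SAP 5.12 match, replacing its open exception with a direct statement of the set used. If as-treated grouping is intended for the exploratory assessments, say so there and exempt hunger. If it is intended for hunger as well, list it in SAP 1.2.4 as a departure from the protocol and amend 3.1.1 and 5.7.2.

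The cost is one sentence in 3.5 and a conforming edit in 5.12, with no new data and no effect on sample size. It should be done before database lock, so that the grouping is not chosen with results in view.
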